4.2.1 Safety data	
4.2.2 Efficacy data	
4.2.3 Demographic and baseline characteristics data	32
5. INTERIM ANALYSES	32
5.1 Data Monitoring Committee	32
6. CHANGES OF ANALYSIS FROM PROTOCOL (NOT APPLICABLE)	33
7. REFERENCES	33
8. APPENDIX	33
8.1 Appendix 1 imAE charter (v6 27Apr2020).	33

LIST OF ABBREVIATIONS

Abbreviation or special term	Explanation
AE	Adverse event
AESI	Adverse event of special interest
ALP	Alkaline phosphatase
ALT	Alanine transaminase
AST	Aspartate transaminase
BMI	Body mass index
BoR	Best Objective Response
CI	Confidence interval
CR	Complete Response
CRF	Case Report Form
CSP	Clinical Study Protocol
CSR	Clinical Study Report
CTC	Common Terminology Criteria
CTCAE	Common Terminology Criteria for Adverse Event
CV	Coefficient of variation
DAE	Discontinuation of investigational product due to adverse events
DBL	Database lock
DCO	Data cut off
DCR	Disease control rate
DMC	Data monitoring committee
DSUR	Development safety update report
ECG	Electrocardiogram
ECOG	Eastern Cooperative Oncology Group
eCRF	Electronic Case Report Form
HL	Hy's Law
ILD	Interstitial lung disease
imAE	Immune-mediated AE
IPD	Important protocol deviation

Abbreviation or special term	Explanation
IV	Intravenous
LDH	Lactate dehydrogenase
MedDRA	Medical Dictionary for Regulatory Activities
NCI	National Cancer Institute
NIH	National Institute of Health
OAE	Other significant adverse events
ORR	Overall response rate
OS	Overall survival
PD	Progressive disease
PD-L1	Programmed death ligand 1
PR	Partial response
PSUR	Periodic safety update report
PT	Preferred term
Q4w	Every 4 weeks
RECIST1.1	Response Evaluation Criteria In Solid Tumors, Version 1.1
SAE	Serious adverse event
SAP	Statistical analysis plan
SD	Stable disease
SI	International system (of units)
SMS	Signal management system
SOC	System organ class
SS	Safety analysis set
Т3	Tri-iodothyronine
T4	Thyroxine
TEAE	Treatment-emergent adverse event
TSH	Thyroid-stimulating hormone
TTE	Time to event
TTR	Time to resolution
ULN	Upper limit of normal
WHO	World Health Organization

AMENDMENT HISTORY

Date	Brief description of change
25May2017	Initial version 1.0
12Jun2020	Amendment v2.0 includes updates consistent with protocol amendment v5.0 regarding DCO and final analysis; clarifications regarding important protocol deviations; additional subgroup analyses for selected endpoints (OS, ORR, DCR, and AEs); and other minor changes to ensure consistency.

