2.2 Protocol Deviations

2.2.1 Important Protocol Deviations

According to ICH E3 guidelines version dated 1995 (ICH 1995),

"Protocol deviations consist of any change, divergence or departure from the study design or procedures defined in the protocol. Important protocol deviations (IPDs) are a subset of protocol deviations that may significantly affect the completeness, accuracy, and/or reliability of the study data or that may significantly affect a patient's rights, safety or well-being."

For the interim analysis, all major deviations were classified as important deviations. For the final analysis, 4 general categories will be considered IPDs and will be listed and summarised.

- Deviation 1: Patients who deviate from key entry criteria per the Clinical Study Protocol v5.0 (CSP).
 - Inclusion Criterion 7: No prior exposure to anti-PD-1 or anti-PD-L1, including on another AstraZeneca study. Exposure to other investigational agents may be permitted after discussion with the Sponsor.
 - Inclusion Criterion 8: Adequate organ and marrow function as defined below:
 - Hemoglobin ≥9.0 g/dL
 - Absolute neutrophil count $\geq 1.0 \times 109 / L$
 - Platelet count \geq 75 × 109/L

- Serum bilirubin ≤1.5 × the upper limit of normal (ULN). This will not apply to patients with confirmed Gilbert's syndrome, who will be allowed in consultation with their physician.
- ALT and AST ≤2.5 × ULN; for patients with hepatic metastases, ALT and AST≤5 × ULN
- Measured creatinine clearance (CL) >40 mL/min or Calculated creatinine clearance (CL) >40 mL/min as determined by Cockcroft-Gault (using actual body weight)
- Inclusion Criterion A1: Histologically or cytologically confirmed locally advanced or metastatic urothelial ornon-urothelial carcinoma of the urinary tract (including the urinary bladder, ureter, urethra and renal pelvis)
- Inclusion Criterion A2: Disease that has progressed during or after at least one previous platinum or non-platinum-based chemotherapy, either for PD less than 12 months after adjuvant or neoadjuvant chemotherapy, or metastatic disease
- Inclusion Criterion A3: ECOG performance status 0-2
- Exclusion Criterion 3: Concurrent enrollment in another clinical study, or another substudy of this protocol, unless it is an observational (non-interventional) clinical study or during the follow up period of an interventional study

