3. PRIMARY AND SECONDARY VARIABLES

3.1 Safety

The primary outcome measure for the study is the number and proportion of patients with AESI. Pre-defined Medical Dictionary for Regulatory Activities (MedDRA) preferred terms groupings will be used to identify AESI.

'On treatment' will be defined as assessments between date of first dose and 90 days following last dose inclusive.

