4.2.1 Safety data

Data from all cycles of treatment will be combined in the presentation of safety data. The following sections describe the planned safety summaries. However, additional safety tables may be required to aid interpretation.

Adverse Events

All AEs will be summarised descriptively, in terms of number of patients (n) and percentage of patients (%) reporting the event by MedDRA system organ class (SOC) and preferred term (PT). The majority of the AE summaries, unless stated otherwise, will be based on TEAEs.

Any adverse events that occur prior to dosing or starting more than 90 days after discontinuing treatment will be presented in a separate summary by SOC and PT.

All reported AEs will be listed along with the date of onset, date of resolution (if AE is resolved) and investigator's assessment of severity and relationship to study drug.

Summary information (the number and percent of patients by SOC and PT) will be tabulated for:

- All TEAEs
- All TEAEs causally related to study medication (as determined by the reporting investigator)
- TEAEs with CTCAE grade 3 or higher
- TEAEs with CTCAE grade 3 or higher, causally related to study medication (as determined by the reporting investigator)
- TEAEs by outcome
- TEAEs with outcome of death
- TEAEs with outcome of death causally related to study medication (as determined by the reporting investigator)
- All treatment-emergent SAEs
- All treatment-emergent SAEs causally related to study medication (as determined by the reporting investigator)
- All treatment-emergent SAEs by maximum NCI CTCAE grade
- TEAEs leading to discontinuation of study medication
- TEAEs leading to discontinuation of study medication, causally related to study medication (as determined by the reporting investigator)
- TEAEs leading to hospitalization
- TEAEs leading to dose interruption of study medication
- Other significant TEAEs
- Other significant TEAEs causally related to study medication (as determined by the reporting investigator)
- Designated medical events
- Infusion reaction TEAEs (as determined by the reporting investigator)

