As well as the overall summary of the number and percentage of patients in each SOC/PT category, an overall summary of the number of episodes in each SOC/PT category will be presented. In addition, a truncated AE table of most common AEs and another table showing most common AEs with CTCAE grade 3 or higher, showing all events that occur in at least 5% of patients overall will be summarised by PT, by decreasing frequency. This cut-off may be modified after review of the data. When applying a cut-off (ie, x %), the raw percentage

will be compared to the cut-off, no rounding will be applied first (i.e., an AE with frequency of 4.9% will not appear if a cut-off is 5%).

An overall summary of the number and percentage of patients in each AE category (Any AE, Any AE causally related to treatment, Any AE of CTCAE grade 3 or higher etc...) will be presented.

Each AE event rate (per 100 patient years) will also be summarised by PT within each SOC for the output summarising all AEs. For each preferred term, the event rate is defined as the number of patients with that AE divided by the total drug exposure of patients at risk of AE. The denominator is the total duration of treatment (in years) across all patients calculated as the sum total (of all patients) of days from first dose to the earlier of the date of first onset of the event or the last day of study medication.

As a part of the trial's Disclosure Record to the National Institute of Health (NIH), the following tables will be produced

- TE non-serious AEs
- TE non-serious AEs causally related to study medication (as determined by the reporting investigator)
- TE non-serious AEs occurring in >5% of Patients
- TE non-serious AEs occurring in >5% of patients causally related to study medication (as determined by the reporting investigator)
- Summary of the number of episodes of treatment-emergent SAE in each SOC/PT category
- Number of subjects enrolled per age group as per EU categories.

Fluctuations observed in CTCAE grades during study will be listed for those TEAEs which are CTCAE > 3.

In addition, all AEs will be listed.

Adverse events of special interest (primary outcome)

Summaries of treatment emergent AESI by category and PT will include number (n) and percentage (%) of patients who have:

- At least one treatment-emergent AESI
- At least one treatment-emergent AESI by outcome
- At least one treatment-emergent AESI leading to treatment interruption or discontinuation

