- At least one treatment-emergent serious AESI
- At least one treatment-emergent AESI by maximum NCI CTCAE grade
- At least one treatment-emergent AESI causally related to study medication
- At least one treatment-emergent AESI with fatal outcome
- At least one treatment-emergent AESI which required additional treatment with steroids, immunosuppressants and hormone replacement therapy
- Laboratory findings, vital signs and other safety parameters associated with AESI will be summarised as part of the AESI outcome measures.

Length of intervention with steroids, immunosuppressants and/or hormone replacement therapy for AESIs will be calculated based on treatment start and stop dates. Total treatment

times will then be combined for each patient and summarised for patients experiencing at least one treatment-emergent AESI.

The exact 95% CIs around the incidence estimates will also be reported for each AESI type.

A summary of total duration (days) of AESI will be provided. For ongoing AESI, the date of death or data cut-off will be imputed as end date.

Immuno-mediated adverse events

Summaries of treatment-emergent imAEs by AESI category and PT will include number (n) and percentage (%) of patients who have:

- At least one treatment-emergent imAE
- At least one treatment-emergent imAE by outcome
- At least one treatment-emergent imAE leading to treatment interruption or discontinuation
- At least one treatment-emergent serious imAEs
- At least one treatment-emergent imAE by maximum NCI CTCAE grade
- At least one treatment-emergent imAE causally related to study medication
- At least one treatment-emergent imAE with fatal outcome

Subgroup analyses

Subgroup analyses will be conducted for the summary of TEAEs in the following subgroups of the SS:

- Sex (male versus female)
- Age at baseline: <65 vs 65-74 vs ≥75 years of age). This will be determined from the date of birth (BRTHDAT in the DM domain) and baseline visit (VIS_DAT in the VISIT domain) on the eCRF. Patients with a partial date of birth (ie for those countries where year of birth only is given) will have an assumed date of birth of 1st Jan [given year]). Patients with a missing age value will be included using the mean age and categorised accordingly.
- Race: Asian vs non-Asian
- ECOG performance status at baseline: 0-1 vs 2
- Tumor histology: Urothelial (i.e. TCC) vs non-urothelial

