- PDL1: high >=25% vs low <25%. If data is available from the central laboratory, the central laboratory result will be used in the group derivation, otherwise, the local test result will be used.

Subgroup analyses will also be conducted for the summary of OS, ORR and DCR in the following subgroups of the SS:

- Age at baseline: <65 vs 65-74 vs ≥ 75 years of age
- ECOG performance status at baseline: 0-1 vs 2
- Primary tumor location: Bladder vs Renal pelvis and Ureter vs Urethra vs Other
- Stage: III vs IV
- Tumor histology: Urothelial (i.e. TCC) vs non-urothelial
- Previous platinum chemotherapy: platinum vs non-platinum chemotherapy
- Best response to previous therapy (CR vs PR vs SD vs PD)

- Baseline metastases: liver (+/- other visceral or non-visceral metastases) vs lymph node metastases only
- PDL1: high \geq 25% vs low \leq 25%

No formal comparisons will be performed between the subgroups.

Time-to-event analyses

Time-to-event of AESI and imAE:

Time-to-onset of AESI/imAE (by AESI/imAE category) and time-to-intervention with steroids, immunosuppressants and/or hormone replacement therapy to treat an AESI/imAE will be defined as time from first dose of durvalumab +/- tremelimumab to first onset of the event.

Time-to-event (TTE) is defined in months as follows:

TTE (months) = (Date of event or censoring–Date first dose of durvalumab [durvalumab + tremelimumab for the combinations modules]+1)/(365.25/12)

Time-to-resolution (TTR) of an AESI/imAE type is defined as the time from the first onset of an AESI/imAE type to the resolution of the AESI/imAE type. TTR is defined in months as follows:

TTR (months) = (Date of AESI/imAE resolution or censoring–Date of AESI/imAE onset+1)/(365.25/12)

Analysis of TTR will only include patients who have experienced an AESI/imAE.

The distribution of TTE and TTR times will be estimated using the Kaplan-Meier method (Kaplan and Meier 1958) and summarised using the median, twenty-fifth and seventy-fifth percentiles. TTE and TTR of imAE of NCI CTCAE grade >=3 will also be produced.

Deaths

A summary of deaths will present number (n) and percentage (%) of patients for the following categories:

- Total number of deaths (including deaths occurring within 90 days after last dose of study medication and deaths occurring after the 90 days post dosing window)

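### Safety subgroup tables omit grouped AESI and imAE, the trial's primary focus, and state no exposure or time-at-risk information to read the percentages against

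*SAP*

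**What the plan says.** SAP 3.1 sets the primary endpoint: "The primary outcome measure for the study is the number and proportion of patients with AESI". SAP 4.2.1 then lists separate summaries for AEs, AESIs and imAEs, with exact confidence intervals for each AESI type. After these lists comes the safety subgroup plan: "Subgroup analyses will be conducted for the summary of TEAEs in the following subgroups of the SS". A second subgroup list covers efficacy: "Subgroup analyses will also be conducted for the summary of OS, ORR and DCR in the following subgroups of the SS". Neither list names AESI or imAE. The SAP amendment history describes the same scope, "additional subgroup analyses for selected endpoints (OS, ORR, DCR, and AEs".

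The default AE measure is a count and percentage: "All AEs will be summarised descriptively, in terms of number of patients (n) and percentage of patients (%) reporting the event". One exposure-based measure is planned: "Each AE event rate (per 100 patient years) will also be summarised by PT within each SOC for the output summarising all AEs". Its person-time is the sum of "days from first dose to the earlier of the date of first onset of the event or the last day of study medication". The SAP does not say whether this rate also appears in the subgroup tables.

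For AESI and imAE the SAP also plans Kaplan-Meier time to onset and, for each AESI category with at least 10 events, prevalence and cumulative incidence plots. Treatment exposure has its own summaries. No subgroup split is stated for any of these. Eligibility, as listed in SAP 2.2.1, is wide on performance status: "Inclusion Criterion A3: ECOG performance status 0-2".

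**The concern.** There are two gaps. First, the plan splits a secondary safety objective, survival and exploratory response by subgroup, but not the grouped primary outcome. Individual AESI preferred terms may appear in the subgroup TEAE tables, but ungrouped and without the exact intervals planned for AESI types. SAP 1.3 itself says the sample size may allow safety to be examined in subgroups.

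Second, the percentage of patients with an event depends on how long each patient is observed. Treatment continues to progression (SAP 1.2) and TEAEs are counted to 90 days after last dose (SAP 3.1.1), so the observation window differs between patients and may differ between subgroups. A group that stops or dies early has less time to show an event. If only n (%) is printed, the reader of an ECOG 0-1 versus 2 table cannot tell lower risk from shorter observation. SAP 4.1 allows the descriptive data to be used as supporting evidence for health authorities, so these tables may carry weight without any formal test.

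**Working it through.** **Plan's own figure.** No document figure bears directly on this point. The only stated probability, over 75% for at least 10 events at 1% incidence in 1,200 patients, reproduces: exact binomial 0.759. At 600 patients, the lower planned size, it is 0.083, and 600 × 1% = 6 expected events before any split.

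**Inputs.** From the documents: TEAE window to 90 days (3 months) after last dose, and a rate denominator ending at first onset or last day of drug. Assumed, because the documents give no exposure, survival or AESI hazard by subgroup: exponential time on drug, death and onset.

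**Crude percentage at equal hazard.** Let h be the monthly onset hazard, a = ln2 / median time on drug, d = ln2 / median survival. The window ends at the earlier of drug time + 3 months and death. Then

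crude = h/(h+d) × (1 − e^(−3(h+d))) + h × e^(−3(h+d)) / (h+d+a).

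- Longer exposure (4 months on drug, 9 months survival), h = 0.05: a = 0.1733, d = 0.0770; 0.1247 + 0.1137 = 0.238, or 23.8%.
- Shorter exposure (1.8 and 3 months), same h: a = 0.3851, d = 0.2310; 0.1013 + 0.0323 = 0.134, or 13.4%.
- Milder contrast (4 and 8 versus 2.5 and 4 months), h = 0.05: 23.0% versus 16.0%.
- First contrast at h = 0.03: 15.5% versus 8.4%.

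To show the same crude percentage, the shorter-exposure group would need a hazard about 1.96 times as high (first contrast) or 1.53 times (milder contrast).

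**Cross-check without death.** With mean drug time m months and a full 90-day follow-up, crude = 1 − e^(−3h)/(1+hm). At h = 0.02 and m = 2 versus 6 it is 9.4% versus 15.9%. Without the 90 days it would be 3.8% versus 10.7%, so the follow-up narrows the gap but does not remove it. Break-even hazard ratios run from 1.26 to 1.78 for m of 2 to 4 versus 6 months and h from 0.01 to 0.05.

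**Would the SAP's rate help?** With time at risk over the full window, the rate is 0.05 × 1,200 = 60 per 100 patient-years in both groups. The SAP's denominator, taking the last day of drug as the earlier of drug stop and death, averages 1/(h+a+d) months: 1/0.3003 = 3.33 and 1/0.6662 = 1.50. If the numerator follows the 90-day TEAE window, as the text suggests, the rates are 0.2385/3.33 × 1,200 ≈ 86 and 0.1336/1.50 × 1,200 ≈ 107. Both exceed 60, and the error now makes the shorter-exposure group look worse.

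**Would a full-window rate be neutral?** Only if the hazard is roughly constant. With an identical front-loaded hazard in both groups (5% per month for 3 months, then 1%; assumed), the first contrast gives crude 15.1% versus 10.8%, but full-window rates of 35 versus 48 per 100 patient-years. The milder contrast gives about 14.8% versus 12.0%, and 36 versus 44.

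**The case against.** The strongest reply has four parts.

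- **No evidence on exposure.** A reader might infer that ECOG 2 patients will look safer than they are. The documents do not support that: they give no exposure, survival or event rate by subgroup, and the subgroup tables hold all-cause TEAEs, which could be more frequent in frailer patients. This stands. The supportable claim is that a short-exposure group can look safer at equal risk.
- **Silence is not exclusion.** A reader might also infer that the subgroup tables are limited by design to crude percentages. The SAP does not say so; it leaves open whether the rate carries over, and it allows additional safety tables. This stands as a matter of wording. But permission is not a specification, and the rate as defined would introduce a different error.
- **Crude incidence is legitimate.** When death competes, n/N over a fully observed window is the actual share of patients who have the event. This stands, and is why n (%) should be kept. It answers a question about burden, though, not about risk per time on treatment, and the reader needs exposure to tell the two apart.
- **Descriptive only.** SAP 4.2.1 rules out formal comparison of subgroups, and OS is shown by the same ECOG and age groups. This limits the stakes, but side-by-side percentages will still be read side by side.

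The point about front-loaded onset also stands: a rate alone is not a neutral remedy. So does the point that splitting every AESI category six ways would give very sparse cells.

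**Conclusion.** The point holds as a specification gap. Grouped AESI and imAE summaries are not planned by subgroup, and the subgroup tables have no stated exposure or time-at-risk information. The possible size of the distortion is about 13% versus 24%, or 16% versus 23% in the milder contrast, at an identical hazard. These figures rest on assumed durations and a constant 5% per month hazard; they show what could happen, not what the trial will show. If exposure turns out similar across subgroups, the distortion disappears and only the missing AESI and imAE tables remain. The overall AESI analysis is not affected by the missing subgroup split.

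**What to change.** In SAP 4.2.1:

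1. Add grouped AESI and imAE (any, grade 3 or higher, serious) to the existing safety subgroup list. Add individual categories only where there are at least 10 events, the threshold already used for the long-term tolerability plots.
2. Keep n (%), and beside it print exposure by subgroup and a time-aware measure. This can be cumulative incidence of first onset at fixed times with death as a competing event, a rate per 100 patient-years, or both. For the rate, time at risk should run from first dose to the earliest of first onset, last dose + 90 days, death or DCO.
3. Use that same denominator for the planned all-AE rate, so the report has one definition, and state whether the rate appears in subgroup tables.
4. Add a note that the rate assumes a roughly constant hazard and can overstate risk in short-exposure groups when onset is early.

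The dates needed are already used elsewhere in the SAP, so no new data collection is required. The cost is more output and some sparse cells. Subgroup results remain descriptive.

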4. ANALYSIS METHODS

4.1 General principles

No hypothesis testing is planned for this single arm study. Each module will be summarised separately.

The general principles as mentioned below will be followed throughout the study:

- Descriptive statistics will be used for all variables, as appropriate, and will be presented separately for each module. Descriptive safety and efficacy data from the STRONG study may be utilized as supporting evidence for health authority considerations.
- Continuous variables will be summarized by the number of observations, mean, standard
 deviation, median, minimum, and maximum. For log transformed data it is more
 appropriate to present geometric mean, coefficient of variation (CV), median, minimum
 and maximum. Categorical variables will be summarized by frequency counts and
 percentages for each category.
- Unless otherwise stated, percentages will be calculated out of the population total.
- Exact CIs for proportions will be calculated using the Clopper-Pearson method.
- For percentiles of survival times based on the Kaplan-Meier method (eg, median survival), CIs will be calculated using the default method available in the SAS LIFETEST procedure (ie, the Klein and Moeschberger extension of the Brookmeyer-Crowley method).
- For point-estimates of survival based on the Kaplan-Meier method (eg, for OS at 12 months), CIs will be calculated using the default method available in the SAS LIFETEST procedure (ie, using Greenwood's estimate of standard error and a log-log transformation).
- For continuous data the mean and median will be rounded to 1 additional decimal place compared to the original data. The standard deviation will be rounded to 2 additional decimal places compared to the original data. Minimum and maximum will be displayed with the same accuracy as the original data.
- For categorical data, percentages will be rounded to 1 decimal place.
- SAS® version 9.3 or higher will be used for all analyses.

Baseline will be the last assessment of the variable under consideration prior to the intake of the first dose of study treatment.

All data collected will be listed.

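### Year-only birth dates are set to 1 January, so any age-group error runs upward; 1 July would roughly halve the errors at almost no cost (minor)

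*SAP*

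**What the plan says.** SAP 4.2.1, under subgroup analyses, defines the age factor for the TEAE summaries as "Age at baseline: <65 vs 65-74 vs ≥75 years of age". It then gives the derivation: "This will be determined from the date of birth (BRTHDAT in the DM domain) and baseline visit (VIS_DAT in the VISIT domain) on the eCRF". Where a country gives only the year, the patient "will have an assumed date of birth of 1st Jan" of the given year.

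The separate list of subgroups for OS, ORR and DCR in the same section repeats the cut-offs ("Age at baseline: <65 vs 65-74 vs ≥ 75 years of age") without repeating the derivation or referring back to it.

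The SAP gives no reason for choosing 1 January, no sensitivity analysis, and no list or count of year-only countries. On use, it says "No formal comparisons will be performed between the subgroups", and SAP 4.1 says "No hypothesis testing is planned for this single arm study".

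**The concern.** 1 January is one end of the range of possible birth dates, not its middle. Every year-only patient is given an age that is equal to or above the true age, so the errors cannot cancel. A patient whose 65th or 75th birthday falls later in the calendar year than the baseline visit is counted as having already reached it. The 75-and-over group can only gain such patients and the under-65 group can only lose them.

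What is at stake is the make-up of the age groups in the TEAE, OS, ORR and DCR tables. SAP 4.1 allows descriptive results to be used as supporting evidence for health authorities, so these tables may be read outside the study team.

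**Working it through.** The plan states no figure for this error, so there is none to reproduce.

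**Inputs from the SAP (4.2.1).** Assumed birth date 1 January; age taken at the baseline visit; cut-offs 65 and 75.

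**Assumptions.** Births spread evenly over the year; baseline visits spread evenly over the year; age at baseline normal with mean 64-70 and SD 8-12. The documents give no age distribution and no enrolment by month.

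**1. Direction.** Imputed age minus true age equals the number of days from 1 January to the true birthday. It runs from 0 to 364 days (365 in a leap year) and is never negative. This needs no assumption.

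**2. Mean error.** (0 + 364)/2 = 182.0 days, or (0 + 365)/2 = 182.5 in a leap year. Divided by 365.25, that is 0.50 year.

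**3. Completed age.** Completed age is one year too high when the birthday falls after the visit day in the calendar year. Over all 365 × 365 pairs of birthday and visit day the share is 364/(2 × 365) = 49.9%; it is never too low. The share depends strongly on the visit date: about 96% for 15 January, 50% for 1 July, 4% for 15 December.

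**4. Share changing group.** With the age error spread evenly between 0 and 1 year, the share crossing cut-off c is the average of F(c) − F(c − s) over s from 0 to 1, which is close to ½f(c), where F is the age distribution and f its density. For mean 68 and SD 10: f(65) = 0.0381 and f(75) = 0.0312, so ½(0.0381 + 0.0312) = 0.0347. Direct evaluation gives 0.0189 + 0.0160 = 0.0348 (rounded). Over the range:

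| Mean age | SD 8 | SD 10 | SD 12 |
|---|---|---|---|
| 64 | 3.5% | 3.1% | 2.8% |
| 66 | 3.8% | 3.4% | 2.9% |
| 68 | 4.1% | 3.5% | 3.0% |
| 70 | 4.1% | 3.5% | 3.1% |

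So 2.8-4.1% of year-only patients move up a group and none move down; about 96-97% stay where they belong.

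**5. The 1 July alternative.** Mean age error is 0.5 to 1 day. Completed age is too high in 12.6% and too low in 12.4% of birthday and visit-day pairs: 25.0% wrong against 49.9%. By half-year of the baseline visit, for three central scenarios (mean/SD 66/10, 68/9, 70/9):

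| Baseline visit | 1 January | 1 July |
|---|---|---|
| January-June | 5.0-5.7% too old | 1.7-1.9% too young |
| July-December | 1.7-1.9% too old | 1.7-1.9% too old (same patients) |
| Whole year, even spread | 3.4-3.8% too old | 1.7-1.9% misplaced, split about evenly |

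The July-December rows agree because by then both assumed birthdays have passed. For a visit at fraction t of the year, the chance of a wrong completed age under 1 January is 1 − t. Under 1 July it is t before mid-year and 1 − t afterwards. The mid-year date is therefore never more error-prone, whatever the visit date.

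**6. Scale (illustration only).** If 10% of 1,200 patients were year-only (an assumed share), that is 120 patients, of whom 120 × 2.8% to 120 × 4.1%, about 3 to 5, would change group. Under 1 July it would be about half as many.

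**The case against.** The rule is prespecified and reproducible, and it matches the SAP's own convention in section 3.1.3, where missing parts of diagnosis dates and partial AE and medication start dates go to the start of the period. No test or formal comparison depends on it, the number of patients affected is unknown and may be tiny, and a mid-year date does not recover true age either. All of that stands, and it is why the point is minor. Consistency with other date rules does not remove the one-way error, however, and the alternative uses the same data and is never worse.

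Four stronger readings are tempting and are not supported:

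- *That year-only patients as a body are moved into older groups.* Only those whose 65th or 75th birthday falls after the baseline visit in the same calendar year are moved.
- *That 1 July leaves no net shift.* That requires baseline visits spread evenly over the calendar year, and the documents give no enrolment by month. If year-only countries enrolled mainly in the second half of a year, most of the upward shift would remain; if mainly in the first half, a smaller downward shift would replace it.
- *That the rule ties age group to country and the change cures it.* Errors are confined to year-only countries under either date, they involve a few percent of those patients, and country is not a planned subgroup factor.
- *That the main safety result is affected.* The primary AESI summaries use the whole safety set and no age grouping.

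**Conclusion.** The point holds as a minor, nearly free improvement. That the error can only be upward follows from the rule itself. The half-year average rests on births being evenly spread. The figure of about 3-4% of year-only patients placed one group too old rests on the assumed age distribution (mean 64-70, SD 8-12) and evenly spread visit dates. The effect on the study as a whole cannot be computed, because the share of year-only patients is not stated. It reaches only the descriptive age subgroups for TEAEs, OS, ORR and DCR.

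**What to change.** In SAP 4.2.1, replace 1 January with 1 July of the given year for patients with only a year of birth, and add that the same derived age is used for the OS, ORR and DCR age subgroups. Do not describe the change as removing bias; it roughly halves misplacement, and balances it only if visits are evenly spread.

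The cost is one phrase in the SAP and one programming constant, with no new data and no change to patient procedures. If the outputs are already final, a footnote giving the number of year-only patients in each age group would let a reader judge the effect.
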